## **8.4. Subgroup Analyses of Efficacy Variables**

The primary efficacy endpoint and the three key secondary efficacy endpoints will be analyzed by doing separate subgroup analyses for the following subgroups: (1) pediatric (age 5 to 17 years) and adult ( $\geq 18$  years) subgroups, (2) among subjects with and without neurotoxic symptoms at baseline as described in [section 8.1](#), (3) among subjects who did and did not complete an initial dose of antivenom prior to randomization, (4) among subjects enrolled in the U.S. and India, (5) among patients bitten by vipers, elapids, and unknown snake types, and (6) among patients for whom the time from bite or symptom onset to receipt of study drug was  $< 5$  hours and  $\geq 5$  hours.

## **9. Safety and Tolerability Analysis**

Safety will be evaluated from reported TEAEs, changes in clinical laboratory values, changes in vital signs, and electrocardiogram (ECG) results, and concomitant medications and therapies.

All safety analyses will be performed on the SAF Population. No inferential statistical tests are planned.

### **9.1. Adverse Events**

All AEs, TEAEs, and SAEs will be coded using the MedDRA thesaurus.

A summary table will present the number and percentage of subjects for each treatment group reporting:

- AEs
- TEAEs
- TEAEs related to IP
- Moderate TEAEs
- Severe TEAEs
- Serious TEAEs
- Serious TEAEs related to IP
- TEAEs resulting in death.

Summaries of the incidence (number and percentage of subjects reporting the TEAE and the number of TEAEs) of TEAEs will be displayed for each treatment group by:

- System organ class, and preferred term
- Maximum severity by system organ class, and preferred term
- Strongest relationship to IP by system organ class, and preferred term.

In the case of multiple occurrences of the same TEAE within the same subject, each subject will only be counted once for each preferred term. However, all multiple occurrences will be included in the number of events. The number of subjects experiencing anaphylaxis or acute hypersensitivity reactions will also be summarized by treatment group. This comparison will be conducted regardless of the determination of causal relationship to the study drug.

In the summaries showing severity and relationship to IP, the event with the maximum severity or strongest relationship will be reported. If a particular event is missing the severity and/or relationship, then the strongest possible severity or relationship will be assumed for analysis.

By-subject AE data listings with all AEs will be displayed.

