To assess the effect of varespladib- methyl on complete blood count (CBC)	CBC through all SSS evaluation days		
To assess the effect of varespladib- methyl on transfusion requirement in patients with hemolysis	Transfusion requirement from Baseline through Day 28		
To evaluate the effect of varespladib-methyl on the levels of C-reactive protein (CRP)	CRP from Baseline through Day 14		
To assess the safety biomarker D- dimer	D-dimer levels from Baseline through Day 14		
To assess the effect of varespladib- methyl on myonecrosis marker (CK) in subjects with and without tourniquets at enrollment	Levels of CK in patients from Baseline through Day 3 in patients presenting with and without tourniquets at enrollment		
To evaluate the levels of secretory phospholipase A2 (sPLA ₂) in serum	• sPLA ₂ in serum at specified timepoints on Days 1 to 7 in all subjects		
Pharmacokinetics Evaluation			
To assess pharmacokinetics (PK) of varespladib-methyl in subjects with snakebite envenoming	PK parameters of varespladib-methyl in plasma from a subset of adult and pediatric subjects at specified timepoints on Days 1 and 3 followed by all subjects pre-dose on Day 7		
Safety	Safety and Tolerability Endpoints		
	• Incidence and severity of adverse events (AEs), serious AEs (SAEs), and AEs leading to discontinuation of Investigational Product (IP)		
	 Safety of varespladib-methyl as assessed by the number and rates of reported treatment-emergent adverse events (TEAEs) from beginning of treatment until last Follow-Up Visit/Telephone call at Day 28 		
	Number of subjects with a treatment-related SAE from beginning of treatment until last Follow-Up		

Objectives	Endpoints
	Visit/Telephone call at Day 28
	 Safety as assessed by Vital signs Clinical laboratory evaluations: CBC, urinalysis, liver function tests [LFTs], renal function tests (albumin, creatinine, blood urea nitrogen [BUN], estimated glomerular filtration rate [eGFR]) 12-lead electrocardiogram (ECG)
	 Concomitant medications and therapies Columbia-Suicide Severity Rating Scale (C-SSRS) evaluated at Baseline or at the earliest time point clinically allowable (ideally Day 1) and then at every study visit through Day 28

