11.2 Event Assessment and Follow-Up of Adverse Events

The occurrence of an AE or SAE may come to the attention of study personnel during study visits and interviews of a study subject presenting for medical care or upon review by a study monitor.

All AEs including local and systemic reactions not meeting the criteria for SAEs will be captured on the appropriate CRF. Information to be collected includes event description, time of onset, clinician's assessment of severity, relationship to study product (assessed only by those with the training and authority to make a diagnosis), and time of resolution/stabilization of the event. All AEs occurring while on study must be documented appropriately regardless of relationship. All AEs will be followed to adequate resolution or stabilization.

OPX-PR-01

Any medical condition that is present at the time that the subject is screened will be considered as Baseline and not reported as an AE. However, if the study subject's condition deteriorates at any time during the study, it will be recorded as an AE.

Changes in the severity of an AE, or an AE that is intermittent, will be documented as separate AEs to allow an assessment of the duration of the event at each level of severity to be performed. AEs characterized as intermittent require documentation of onset and duration of each episode.

Site staff will record all reportable AEs with start dates occurring any time after informed consent is obtained until 28 days after the last day of study participation. At each study visit, the Investigator will inquire about the occurrence of AE/SAEs since the last visit.

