13.1.6.1 Adverse Events

Treatment-emergent AEs are defined as AEs that first occur or worsen in severity after the first dose of IP and prior to the 30 days after last administration of IP. AEs will be coded using the Medical Dictionary for Regulator Activities (MedDRA). For each treatment group, the number of TEAEs and incidence rates will be tabulated by preferred term and System Organ Class.

Treatment-emergent AEs will be summarized for each treatment group based on frequency, maximum severity, relationship to IP, SAEs, TEAEs leading to death, and TEAEs leading to discontinuation of IP.

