#### **6.1.7.12. Treatment-Emergent Adverse Event**

Treatment-emergent AEs are defined as AEs that first occur or worsen in severity after the first dose of IP and prior to 30 days after last administration of IP.

Where an AE start date/time or end date/time is partially or fully missing, and it is unclear as to

whether the AE is a TEAE, it will be assumed that it is TEAE.

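### Each change in an adverse event's severity opens a new AE record and the SAP has no rule to link them, so the number of TEAEs partly reflects how often severity was re-graded

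*SAP*

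**What the plan says.** **How AEs are recorded.** Protocol 11.2: "Changes in the severity of an AE, or an AE that is intermittent, will be documented as separate AEs". The rule covers changes in either direction. Its stated purpose is to measure how long an event lasts at each grade.

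**What is counted.** SAP 9.1: "Summaries of the incidence (number and percentage of subjects reporting the TEAE and the number of TEAEs) of TEAEs will be displayed". For repeats within a subject it has two rules. For subject counts, "each subject will only be counted once for each preferred term". For event counts, "However, all multiple occurrences will be included in the number of events". Protocol 13.1.6.1 plans the same output: "the number of TEAEs and incidence rates will be tabulated by preferred term and System Organ Class".

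**Why the count has standing.** Protocol Section 6 lists as a safety endpoint the "number and rates of reported treatment-emergent adverse events (TEAEs) from beginning of treatment until last Follow-Up Visit/Telephone call at Day 28". SAP 2.2.2 repeats it.

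**What makes an AE treatment-emergent.** SAP 6.1.7.12 covers "AEs that first occur or worsen in severity after the first dose of IP", up to 30 days after the last dose. Protocol 11.1.4 is similar. Neither says how to classify a record that was opened because severity fell.

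**What is collected.** Protocol 11.2.3 requires start and stop date and time, and severity, for each AE. It lists no field that ties one record to another.

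**The concern.** A recording device meant to measure duration by grade feeds an endpoint that counts events. One continuing episode becomes several records. The SAP puts repeats into the event count and does not say whether a severity segment is a repeat.

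Two things are at stake. First, the event count mixes how many events occurred with how often they were re-graded. Secondly, the counting unit is undefined: two programmers who follow both documents in good faith could report different numbers of TEAEs from the same database.

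The schedule gives room for re-grading. Table 1 of the protocol has serum chemistry at eight post-dose timepoints and liver function tests at five. Protocol 11.1.1 always treats a clinically significant liver or renal laboratory abnormality as an AE if it has worsened from baseline. Protocol 5.3 describes modest, transient liver-enzyme increases in earlier studies, and a rise and fall is a pattern that this rule splits.

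**Working it through.** The documents state no figure on this point, so there is none to reproduce. The check is a count of records per episode.

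**Step 1: count per episode.** Inputs: the splitting rule (Protocol 11.2), the event-count rule (SAP 9.1) and the TEAE definition (SAP 6.1.7.12). Take an episode that starts after the first dose.

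- Broad reading, in which every record is a TEAE because each separate AE has its own post-dose start: count = 1 + number of severity changes.
- Narrow reading, in which only onset and worsening are TEAEs: count = 1 + number of upward changes.
- Segments linked and merged: count = 1.

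| Course of one episode | Broad | Narrow | Merged |
|---|---|---|---|
| Severe throughout | 1 | 1 | 1 |
| Moderate, mild | 2 | 1 | 1 |
| Severe, moderate, mild | 3 | 1 | 1 |
| Mild, moderate, mild | 3 | 2 | 1 |
| Mild, moderate, severe | 3 | 3 | 1 |
| Mild, moderate, severe, moderate, mild | 5 | 3 | 1 |

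The narrow reading removes the step-down records but still counts a worsening episode more than once.

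**Step 2: possible effect on the arms.** Every input here is assumed. The documents give no frequency of severity changes and no difference between arms. Take 40 true episodes in each arm, so the true ratio is 1.0.

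*Step-downs.* All episodes start severe, and a share f passes through both lower grades. Broad count = 40 × (1 + 2f).

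- f = 0.25 in both arms: 60 and 60, ratio 1.0.
- f = 0.50 and 0.25: 80 and 60, ratio 1.33.
- f = 0.75 and 0.25: 100 and 60, ratio 1.67.
- f = 1 and 0, the extreme: 120 and 40, ratio 3.0.

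On the narrow reading, all four cases give 40 and 40.

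*Step-ups.* All episodes start mild, and a share g worsens once. Count = 40 × (1 + g) on either reading. With g = 0.50 and 0.25, the counts are 60 and 50, ratio 1.20. Here the arm with more deterioration has more events.

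The distortion can therefore run either way, and it vanishes from the ratio when the mean number of counted changes per episode is equal.

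**Step 3: which outputs are exposed.**

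- Exposed: the number-of-events column in the TEAE incidence tables.
- Not exposed: percentages of subjects (one count per subject and preferred term), the overall summary in SAP 9.1 (subjects only), the severity summaries (highest grade reported) and the FDA Medical Query tables in SAP 9.1.3 (subjects).
- SAP Section 9 plans no inferential safety test, and no rate ratio is specified.

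**The case against.** **The TEAE definition already excludes step-downs.** A record opened because severity fell is, in plain terms, neither a first occurrence nor a worsening, and a lower-grade segment is not naturally another occurrence. The SAP never mentions severity-split records. This is a fair reading and it may be what the sponsor intends. But applying it requires knowing that the record continues an earlier one, and neither document provides that link. It also leaves worsening episodes counted more than once.

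**A reader might infer that improvement is counted as harm, so that an effective drug would look less safe.** The documents do not support this. Step-downs count only on the broad reading. Worsening is split too, so a deteriorating arm gains events, and a drug that prevents escalation would lose them. An event that goes straight from severe to resolved gives one record. Under Protocol 11.2, conditions present at screening are baseline and are not AEs unless they deteriorate, so stepwise recovery from the presenting envenoming adds no records.

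**A reader might also infer that the liver and kidney safety findings are distorted.** Hepatic injury and acute kidney injury have their own subject-level queries in SAP 9.1.3, which splitting does not touch. The renal toxicity described in Protocol 11.3.3 comes from preclinical studies.

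**The affected output is small and descriptive.** This stands. The count appears beside unaffected subject counts, every AE is listed, and SAP 9.1.1 uses incidence rates to mean frequencies and percentages. It limits the importance of the point. A named endpoint still needs a defined counting unit.

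**Conclusion.** The point holds as a gap in the counting rule. One continuing episode can enter the number of TEAEs twice through onset and a single worsening. It can enter three or more times with further worsening, or if step-down records are also taken as first occurring after dosing. The count therefore depends partly on how often severity was re-graded.

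The per-episode figures follow from the two rules read together. The SAP does not itself say that severity segments are events, so this is the result of an unstated rule and not of an explicit instruction. The ratios between arms (1.20 to 3.0 where the arms differ) rest wholly on assumed shares and show only what is possible. From the documents, neither the direction nor the size of a difference between arms can be known.

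The consequence is limited to descriptive event counts. It is worth correcting because those counts belong to a stated safety endpoint and the correction is cheap. It is a counting convention and does not concern clinical management.

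**What to change.** Make two changes to the SAP before database lock, while the team is still blinded.

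1. **SAP 6.1.7.12.** Assign treatment-emergent status to each record first. State that a record opened only because severity decreased is not a new TEAE. State that an AE which began before dosing and worsened after the first dose remains a TEAE. The order matters: AEs are collected from consent, so merging first would give such an AE a pre-dose onset and could drop it.
2. **SAP 9.1.** Then count contiguous records of the same subject and preferred term that differ only in severity as one event, at its maximum post-dose severity. Define contiguous as the next record starting at, or directly after, the previous stop. Judge this on all records of the episode, including step-downs. Recurrences after a gap still count separately.

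Keep the split records for listings and for duration by severity, which is why the protocol asks for them.

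The cost is one extra derivation from start and stop times already collected, and slightly lower event counts. Sites do nothing new.

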#### **9.1.1. Adverse Events Leading to Withdrawal**

A summary of incidence rates (frequencies and percentages) of TEAEs leading to withdrawal of IP, by treatment group, system organ class, and preferred term will be prepared for the SAF Population.

A data listing of AEs leading to withdrawal of IP will also be provided, displaying details of the event(s) captured on the eCRF.

### **9.1.2. Deaths and Serious Adverse Events**

Any deaths that occur during the study will be listed. Moreover, all-cause mortality will be analyzed as described in [Section 8.2.12](#).

Serious adverse events will be listed and tabulated by system organ class and preferred term and presented by treatment.

### **9.1.3. FDA Medical Queries**

The number and percentage of subjects experiencing the following FMQs will be reported by treatment group. Construction of each item will be based on the PTs specified at <https://www.regulations.gov/docket/FDA-2022-N-1961/document>.

- Hepatic Injury (Narrow and Broad)
- Acute Kidney Injury (Narrow and Broad)
- Stroke and TIA (Narrow and Broad)
- Myocardial Ischemia (Narrow)
- Arrhythmia (Narrow)
- Cardiac Conduction Disturbance (Narrow)
- Hypersensitivity (Standard Narrow and Broad)

## **9.2. Vital Signs**

Descriptive summaries of actual values and changes from baseline will be calculated for all vital signs including systolic blood pressure, diastolic blood pressure, heart rate, respiratory rate, and body temperature.

## **9.3. Clinical Laboratory Evaluations**

The number of subjects with clinical laboratory values (chemistry, hematology, urinalysis) below, within, or above the normal range by visit and in relation to baseline will be tabulated for each clinical laboratory analyte (shift table). Continuous summaries of observed values and changes from baseline will also be reported. Denominators of the percentages will be the number of subjects in the SAF Population.

All laboratory test results, including coagulation and hematological function tests, will be displayed in by-subject listings and those that are outside the normal range will be flagged, along with corresponding normal ranges.

By-subject pregnancy test results will be listed.

## **9.4. Vital Signs**

Descriptive summaries of actual values and changes from baseline will be calculated for all vital signs (systolic blood pressure, diastolic blood pressure, heart rate, respiratory rate, and body temperature).

### **9.5.      Electrocardiograms**

The number and percentage of subjects with normal and abnormal ECG results will be summarized for the SAF Population by treatment group. Summaries of observed values and change from baseline will also be reported.

### **9.6.      Physical Examination**

The number and percentage of subjects with normal, abnormal clinically significant, and abnormal not clinically significant physical examination results by body system will be summarized for the SAF Population by treatment group.

### **9.7.      Concomitant Medication**

Prior and concomitant medications by Anatomical Therapeutic Chemical (ATC) level 3 will be summarized descriptively by treatment group using counts and percentages.

Prior medications will be presented separately from concomitant medications. Medications that started before the first drug use will be considered prior medications whether or not they were stopped before the first IP. Any medications continuing or starting after the first drug use will be concomitant. If a medication starts before the first drug use and continues after the first drug use it will be considered both prior and concomitant. Where a medication start date or end date is partially or fully missing, and it is unclear as to whether the medication is prior or concomitant, it will be assumed that it is concomitant.

Concomitant use of analgesics will also be summarized and presented separately.

Medications will be coded using the latest WHO-DD version.

### **9.8.      Columbia-Suicide Severity Rating Scale**

The C-SSRS items will be tabulated by treatment group and visit.

## **10.      Changes from Planned Analysis**

Several changes have occurred since version 1.0 of the SAP. For example, multiple imputation and fixed-sequence testing were added in SAP v3.0; and the FMs and additional sensitivity analysis on the primary endpoint were added in SAP v4.0. More details are provided in the Document History section above. All changes were made while the study team was blind to treatment assignment and prior to database lock.

## **11.      Other Planned Analysis**

## 11.1. Pharmacokinetic Analysis

Descriptive summaries of the concentration level of varespladib-methyl in plasma and sPLA2 activity at specified timepoints will be tabulated by treatment group.

By-subject concentrations of varespladib-methyl in plasma will also be presented.

The pharmacokinetic characterization of drug concentrations for each dose to be profiled will be performed using noncompartmental analysis (NCA).

The PK parameter estimates will be completed using Phoenix WinNonlin (Pharsight Corporation) software using the actual elapsed times from dose administration to sample collection. For plasma concentration data, all values below the limit of quantification (BLQ) will be set to 0 for summary statistics and graphs. For the PK parameter calculation, BLQ plasma concentrations occurring before Tmax will be set to 0, with the exception of a BLQ value occurring between two measurable concentrations, in which case it will be set to missing.

Standard PK parameters assessed will include measures of the extent of absorption using estimates of the area under the plasma concentration-time curve from time 0 to the time of the last quantifiable plasma concentration (AUC0-t), Area under the plasma concentration-time curve from time 0 to infinity (if data permits) (AUC0-inf) and rate of absorption using the maximum serum plasma concentration (Cmax), the time of Cmax (Tmax), apparent first order terminal elimination half-life (t1/2), apparent terminal phase rate constant ( $\lambda_z$ ) (if data permits). Any subject for whom the portion of the AUC extrapolated to infinity exceeds 20% of the total AUC0-inf will be excluded from the calculation of the descriptive statistics for AUC0-inf.

Other PK parameters may be derived, where appropriate, and as data permit.

For noncompartmental analysis, plasma concentrations will be listed and summarized at each time point using descriptive statistics. Descriptive statistics reported will include the arithmetic mean, SD, CV%, geometric mean, minimum, maximum, and median. Only the range and the median will be reported for Tmax and Tlast, as these are categorical parameters. The PK parameters will also be summarized by treatment using descriptive statistics.

Individual plasma concentration plots and mean data graphs will be produced using both linear and semi-logarithmic scales. Mean data graphs will show plasma concentration profiles by treatment group. Pharmacokinetic parameter estimates and summaries will be completed for the subjects in the PK population.

Exploratory analysis to correlate PK endpoints with sPLA2 activity may be conducted and documented in a separate analysis plan.

The PK analyses will be performed by a third-party central lab.

## 11.2. Pharmacoeconomic Analysis

Pharmacoeconomic analyses will be conducted to estimate the effect of varespladib treatment on the cost of care. These analyses will include, but are not limited to, the amount of antivenom given to the patient and the duration of hospital stay.

